3.0 Study Design

This is a Phase II therapeutic trial combining Decitabine days 1-5 with oral Vorinostat twice daily days 6-15 followed by a single infusion of CD3-/CD19-enriched donor NK cells on day 17 and a short course of Interleukin-2 (IL-2) to facilitate NK cell survival and expansion. Two courses of treatment will be given separated by 6 - 8 weeks. Clinical response will be formally assessed 4 - 6 weeks after the 2nd course based on International Working Group (IWG) criteria;

however, a bone marrow evaluation will be done if the patient is taken off treatment prior to study completion. **The intent is to administer all treatment in the outpatient setting.**

The trial will use Simon's two-stage design. Fifteen patients will be enrolled in stage 1. If 6 or more of the patients achieve an objective clinical response (CR + PR + hematologic improvement (HI)), stage 2 will be activated and an additional 31 patients enrolled for a total of 46 evaluable patients. Considering a predicted dropout rate of 10% during the two courses of therapy, stage 1 will need a maximum of 17 patients or a maximum of 51 patients if the study proceeds to 2nd stage.

Research and related correlative studies will be done at baseline, between courses 1 and 2, and after completion of course 2 as per section 8.1.2.

4.0 Selection of Patients

Study entry is open to adults regardless of gender or ethnic background. While there will be every effort to seek out and include females and minority patients, the patient population is expected to be no different than that of other studies of high risk myelodysplastic syndromes at the University of Minnesota and the Mayo Clinic.

Inclusion Criteria:

- 4.1 Diagnosis of high risk MDS that meets one of the following disease classifications and is requiring treatment:
 - 4.1.1 International Prognostic Scoring System (IPSS) Category: INT-2 or High Risk (see Appendix IV)
 - 4.1.2 International Prognostic Scoring System- Revised (IPSS-R) Category: High or Very High (Score of 5 or above) (Appendix IV)
 - 4.1.3 WHO Classification: RAEB-1 or RAEB-2 (Appendix V)
 - 4.1.4 WHO Classification: CMML that is not highly proliferative; WBC < 15k
 - 4.1.5 High risk cytogenetic abnormality as defined by presence of Monosomy 7, complex karyotype, or monosomal karyotype
 - 4.1.6 Therapy related MDS
 - 4.1.7 Severe cytopenias: Neutropenia (ANC \leq 0.8), platelet or PRBC transfusion dependent
 - 4.1.8 WHO Based Prognostic Scoring System (WPSS): High or Very High Risk (Appendix V)
- 4.2 Prior Treatment:
 - 4.2.1 Untreated/Minimally Treated: maximum of 2 cycles of hypomethylating agents (azacitidine or decitabine) without evidence of treatment failure as defined by progression to more advanced MDS Who classification or AML.

- 4.2.2** Treatment Failure: Patients who have not responded to or whose disease has progressed on hypomethylating agents (azacitidine or decitabine), 7+3 type induction chemotherapy, or immunosuppressive therapy such as ATG+CSA.
- 4.2.3** Patients must not have received treatment for their MDS within 4 weeks of beginning this study.
- 4.3** Age \geq 18 years of age
- 4.4** ECOG Performance Status 0-2 (Appendix III)
- 4.5** Available related HLA-haploidentical NK cell donor by at least Class I serologic typing at the A&B locus
- 4.6** Have acceptable organ function as defined below within 14 days (28 days for cardiac) of enrollment:
 - Renal: Creatinine: \leq 2.0 mg/dL
 - Hepatic: SGOT/SGPT $<$ 5 x upper limit of institutional normal (ULN)
 - Pulmonary: oxygen saturation \geq 90% on room air
 - Cardiac: LVEF by ECHO or MUGA \geq 40%, no uncontrolled angina, severe uncontrolled ventricular arrhythmias, or electrocardiographic evidence of acute ischemia or active conduction system abnormalities. QTc $<$ 500 msec
- 4.7** Ability to be off prednisone and other immunosuppressive drugs for at least 3 days prior to the NK cell infusion (excluding pre-meds)
- 4.8** Women of child bearing potential must agree to use effective methods of contraception (diaphragm, birth control pills, injections, intrauterine device [IUD], surgical sterilization, subcutaneous implants, or abstinence, etc.) from the time of signing the consent form and for 2 months after the last dose of chemotherapy.
- 4.9** Voluntary written consent before performance of any study-related procedure not part of normal medical care, with the understanding that consent may be withdrawn at any time without prejudice to future medical care.

Exclusion Criteria:

- 4.10** Pregnant or lactating. The agents used in this study are known to be teratogenic to a fetus and there is no information on the excretion of agents into breast milk. Confirmation that the patient is not pregnant must be established by a negative pregnancy test result obtained during screening. Pregnancy testing is not required for surgically sterilized or post-menopausal women.
- 4.11** New progressive pulmonary infiltrates on screening chest x-ray or chest CT scan that has not been evaluated with bronchoscopy (when feasible)
- 4.12** Uncontrolled bacterial or viral infections - chronic asymptomatic viral

hepatitis is allowed

- 4.13** Pleural effusion moderate to large in size that are detectable on chest x-ray
- 4.14** Known hypersensitivity to one or more of the study agents
- 4.15** Prior hypomethylating treatment greater than 2 cycles or with documented treatment failure
- 4.16** Prior use of histone deacetylase inhibitors
- 4.17** Serious medical or psychiatric illness likely to interfere with participation in this clinical study in the opinion of the enrolling investigator
- 4.18** Inability to swallow capsules
- 4.19** Active HIV
- 4.20** Other active and potentially life threatening malignancy excluding localized basal or squamous cell skin cancer, cervical carcinoma in situ, superficial bladder cancer, localized prostate cancer

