2.3 Rationale for Proposed Study

Based on the high single agent efficacy of Decitabine as a standard initial MDS therapy, the numerous studies suggesting a synergistic anti-tumor effect in MDS with HDAC inhibitor Vorinostat, and the potential immunosuppressive impact of Vorinostat, we propose the following therapeutic platform. Sequential Decitabine and Vorinostat will provide the basis for both a disease specific therapeutic and immunosuppressive conditioning regimen to allow for transient host acceptance of donor NK cells for added anti-tumor effect. Dosing of sequential Decitabine (10 mg/m² Days 1-5) and Vorinostat therapy (200 mg twice daily Days 6-15) is based on Phase I studies of the combination detailing the best delivery and tolerance of the combination with the fewest treatment delays³⁶ and early phase studies identify responses in MDS and AML patients.^{37,38} After haploidentical NK infusion, subsequent lower dose IL-2 will be given to promote NK cell expansion and predicted anti-tumor effect. The less intense conditioning regimen and IL-2 cytokine therapy is predicted to be more tolerable in an older population of patients and feasible in the outpatient setting. However, given the diminished intensity of the regimen, and the need for subsequent cycles of hypomethylating agent therapy to observe consistent clinical responses in the general practice setting, the study will consist of 2 consecutive courses (cycles) of therapy.

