7.6 Second Treatment Course

Any patient who failed prior treatment (i.e. met section 4.2.2 of the eligibility criteria at enrollment) will have a bone marrow biopsy and aspirate performed prior to the start of the 2nd treatment course.

A second treatment course will be given 6 to 8 weeks after the start of course 1, identical to the first course substituting the frozen NK cell product for the fresh product, unless medically unsafe.

The following criteria must be met before a new treatment course is started:

- ANC recovery to baseline documented prior to course 1
- Platelet transfusion that can be managed safely in the outpatient setting

- Treatment related non-hematologic toxicity, except fatigue, alopecia, resolved to \leq grade 2
- Absence of rapid disease progression as defined in Section 7.10

If the above requirements are not met, delay and reassess weekly until recovery occurs. If more than 2 weekly delays occur (>8 weeks from the start of course 1) without hematological recovery and/or non-hematologic treatment related toxicity resolution, the patient will be taken off study. A bone marrow biopsy will be done to assess response to the therapy up to that point or to determine etiology for inadequate recovery of counts.

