8.0 Study Calendar

The pre-treatment work-up must occur within 28 days (14 days for CBC, diff, CMP, and chemistries) of treatment start unless otherwise noted. Scheduled evaluations (including research samples) up to day +22 may be performed +/-1 day from the targeted date; evaluations and procedures (including research samples) performed after day +28 may be done +/-3 days of the targeted date. Follow-up for survival may be done +/- 4 weeks of the targeted date. In addition, targeted days may be altered as clinically appropriate.

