Appendix VI – MDS Response Criteria

Based on International Working Group 2006 Modified Criteria

- Complete Remission (CR): $< 5\%$ myeloblasts with normal maturation of all cell lines
 - Persistent dysplasia will be noted
 - Peripheral Blood:
 - Hgb $\geq 11\text{g/dl}$
 - Platelets $\geq 100 \times 10^9/\text{L}$
 - Neutrophils ≥ 1000
 - Blasts = 0%
- Partial Remission (PR): all CR criteria if abnormal before except:
 - BM blasts decreased by $\geq 50\%$ over pre-treatment but still $>5\%$
- Marrow CR: Bone marrow with $\leq 5\%$ myeloblasts and decrease by $\geq 50\%$ over pretreatment with incomplete peripheral blood count normalization
- Hematologic Improvement (HI):
 - Hgb: Increase by $\geq 1.5\text{g/dl}$ or decreased PRBC transfusions by at least 4/8 week period (only PRBC given for Hgb $<9.0\text{g/dl}$)
 - Platelet Response: Absolute increase of $\geq 30 \times 10^9/\text{L}$ for those starting at $>20 \times 10^9/\text{L}$ For those $< 20 \times 10^9/\text{L}$ at baseline increase by 100% .
 - Neutrophil Response: at least 100% increase and an absolute increase of $>0.5 \times 10^9/\text{L}$
- Stable Disease: Failure to achieve at least a PR but no evidence of disease progression for >8 weeks
- Failure: Death during treatment or disease progression characterized by worsening cytopenias, increase percentage of marrow blasts, or progression to a more advanced MDS FAB subtype
- Cytogenetic Response:
 - Complete: Disappearance of any pre-treatment chromosomal abnormalities without the appearance of new ones
 - Partial: At least 50% reduction of chromosomal abnormality
- Disease Progression: Compared to pre-treatment values
 - Less than 5% blasts: greater than 50% increase to $>5\%$ blasts
 - $5\text{-}10\%$ blasts: greater than 50% increase to $>10\%$ blasts
 - $10\text{-}20\%$ blasts: greater than 50% increase to $>20\%$ blasts

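### CR has no baseline condition and HI has no defined baseline, so earlier MDS therapy, or recovery from it, can score as response in the primary endpoint

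*Combined protocol and SAP*

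**What the plan says.** Section 4.2.1 accepts a "maximum of 2 cycles of hypomethylating agents (azacitidine or decitabine) without evidence of treatment failure", where failure means progression to a more advanced WHO class or to AML. Section 4.2.2 separately accepts "Patients who have not responded to or whose disease has progressed on hypomethylating agents (azacitidine or decitabine), 7+3 type induction chemotherapy", and failures of immunosuppression. Section 4.2.3 sets the only washout: "Patients must not have received treatment for their MDS within 4 weeks of beginning this study". Nothing in Section 4 asks for counts to have recovered from that treatment.

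For the baseline, Section 8.0 states: "The pre-treatment work-up must occur within 28 days (14 days for CBC, diff, CMP, and chemistries) of treatment start unless otherwise noted". Footnote 1 to the table in 8.1.1 excuses the course 1 Day 1 evaluations when screening was done in the preceding 14 days.

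Appendix VI defines CR as fewer than 5% "myeloblasts with normal maturation of all cell lines", plus fixed limits for hemoglobin, platelets, neutrophils and blood blasts. PR and HI are worded as changes. CR, PR and HI all count toward the primary endpoint (Sections 9.0 and 13.1). Section 9.0 plans one comparison by prior treatment, with untreated and minimally treated patients combined on one side and treatment failures on the other.

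**The concern.** The primary objective is the response rate produced by two courses of this regimen, and both Simon decisions rest on it. In a single-arm trial, any response that comes from earlier treatment is credited to the regimen. The written rules leave two ways for that to happen.

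- **CR route.** A patient improving on one or two hypomethylating cycles is eligible. If that patient already meets the CR thresholds at study baseline and stays there, Appendix VI records a CR. Section 2.3 justifies two courses by "the need for subsequent cycles of hypomethylating agent therapy to observe consistent clinical responses in the general practice setting", so a response to earlier cycles may also still be developing at entry.
- **HI route.** If the baseline count is taken while marrow is still suppressed by the previous therapy, its recovery can look like hematologic improvement.

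The planned comparison would not show the CR route, because the patients it affects are pooled with untreated patients.

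**Working it through.** **1. The plan's own design.** Inputs from Section 13.1: 15 patients in stage 1, stop at 5 or fewer responders; 46 in total, unworthy at 18 or fewer; p0 = 0.30, p1 = 0.50. With b the binomial probability,

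P(pass) = Σ over x = 6 to 15 of b(x; 15, p) × P(Bin(31, p) ≥ 19 − x).

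- p = 0.30: stage 1 passed with probability 0.278, both stages 0.0499.
- p = 0.50: stage 1 passed with probability 0.849, both stages 0.803.

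The stated 5% and 80% are reproduced. The 5% assumes that every counted response beyond the null rate comes from the regimen.

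**2. Timing of the baseline count.** The last prior dose may be 28 days before the study begins (4.2.3), and the CBC may be up to 14 days before treatment start (8.0). If the study begins on Day 1, the earliest permitted baseline count is 28 − 14 = 14 days after prior therapy. If the washout runs to enrollment and treatment starts d days later, it is 14 + d days. Footnote 1 means that no later count before treatment is required.

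**3. Which response categories look back to baseline (Appendix VI).**

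| Category | Comparison with baseline | Exposure |
|---|---|---|
| CR | None; absolute thresholds only | Can be met before the first study dose |
| PR | Applies to values abnormal beforehand; blasts must fall by at least 50% | Cannot be met without a change |
| HI | Hgb +1.5 g/dl, platelets +30 × 10⁹/L (if starting above 20), or neutrophils doubled and up by more than 0.5 × 10⁹/L | Baseline date not defined; no minimum duration stated for the rise in counts |

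**4. Illustration of the effect.** The documents give no carry-over rate, so these are assumptions. Let the true response rate be 30% in all patients, s the share recently treated, and q the chance that a recently treated non-responder scores falsely. The apparent rate is p = 0.30 + 0.70 × s × q.

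| s | q | Apparent rate | Pass stage 1 | Pass both stages |
|---|---|---|---|---|
| 0 | – | 30.0% | 27.8% | 5.0% |
| 10% | 20% | 31.4% | 32.1% | 7.4% |
| 20% | 20% | 32.8% | 36.5% | 10.6% |
| 30% | 30% | 36.3% | 47.8% | 22.0% |

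**The case against.** Several limits on this concern are real.

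- **Entry at CR is restricted.** Section 4.1 requires high-risk disease that needs treatment, and the work-up includes a marrow. A reader might infer that patients in remission qualify freely on their diagnostic label; the documents do not say so. Still, karyotype, WHO class and therapy-related MDS (4.1.5, 4.1.3, 4.1.6) carry no threshold for blasts or counts at study baseline, so the case is uncommon rather than excluded.
- **7+3 patients must be failures.** Carried-over remission does not apply to them; only count recovery does.
- **Fourteen days is the extreme.** It needs the last prior dose, the CBC date and the start of study all at their limits. The protocol nonetheless permits it.
- **The direction of the HI bias is not certain.** Section 7.8.4 expects pancytopenia from the regimen. If it persists at the response assessment, it would lower HI and CR. This may offset part of the HI route, but it does not supply CR with a baseline condition.
- **The null rate might already contain such responses.** Section 13.1 gives no basis for the 30%, so this cannot be assumed either way.

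Section 7.6 might tempt a reader to a stronger claim. It takes patients off study with "If more than 2 weekly delays occur (>8 weeks from the start of course 1) without hematological recovery", which could suggest that the protocol regards 2 to 4 weeks as too short for recovery. But that clock runs from the start of the course, not from the last dose. Course 2 may begin at 6 weeks, about day 43. That is 28 days after the last vorinostat (day 15) and 21 days after the last IL-2 (day 22). The inference does not follow.

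**Conclusion.** The concern holds as a gap in endpoint and baseline wording, with a bias of unknown size. CR can be credited without any change during the study, and HI can be measured from a count taken 14 days after prior therapy. Under moderate assumed carry-over, the chance of wrongly passing both stages goes from 5.0% to 7.4%, 10.6% or 22.0%. These figures assume a uniform 30% true rate, the same patient mix in both stages, and no offset from the regimen's myelosuppression.

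A reader might go further and suppose that a fraction f of all evaluable patients scores through carry-over with certainty, so that p = f + (1 − f) × 0.30. That gives 12.5% at f = 5% and 57.4% at f = 20%. The arithmetic is right, but the documents do not support a false-scoring fraction that large. At f = 20%, for example, half of accrual would have to be recently treated and 40% of those would have to score falsely. Nor do the documents show that both Simon decisions are in fact biased upward; they show only that the rules allow it.

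**What to change.** 1. In Appendix VI, count CR toward the primary endpoint only if the CR criteria were not met at study baseline, judged on the pre-treatment marrow and baseline CBC. The same condition has no meaning for PR or HI, which already require a change.
2. In 8.1.1, remove the footnote 1 waiver of the Day 1 CBC for patients with prior MDS therapy. For all patients, define the HI baseline as the last CBC before the first decitabine dose (Day 1 where taken). In pretreated patients this moves the shortest gap from 14 to about 28 days. Taking the higher of two counts in pretreated patients alone should be avoided, because it adds a downward bias in one subgroup.
3. In Section 9.0, report response descriptively in three groups: no prior hypomethylating agent, one to two cycles without failure, and treatment failure.
4. Reconcile exclusion 4.15, "Prior hypomethylating treatment greater than 2 cycles or with documented treatment failure", with inclusion 4.2.2. The two contradict each other on hypomethylating failures, so the size of that group is unclear. Exclusion 4.15 does not close the route through one to two cycles without failure, or the route through 7+3.

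The cost is some wording and one Day 1 CBC that is already a calendar item. The reported response rate may be lower. Items 1 to 3 change no dose or eligibility rule.

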- Therapy related MDS
- Severe cytopenias: Severe neutropenia (ANC \leq 0.8), platelet or PRBC transfusion dependent
- WHO Based Prognostic Scoring System (WPSS): High or Very High Risk

Prior treatment:

- Untreated/Minimally Treated: May be untreated or have had a maximum of 2 previous cycles of hypomethylating agents (azacitidine or Decitabine) **without** evidence of treatment failure
- Treatment Failure: Patients who have not responded to or whose disease has progressed on hypomethylating agents (azacitidine or decitabine), 7+3 type induction chemotherapy, or immunosuppressive therapy such as ATG+CSA

Age \geq 18 years of age, ECOG 0-2, adequate renal, hepatic and cardiac function as defined in section 4.6
Available related HLA haploidentical NK cell donor age 18-75 years

[figure not shown]
Accrual Objective:

Stage 1 – 15 evaluable patients; Stage 2 activate if \geq 6 of stage I patients achieve response. If so, then enroll an additional 31 patients for a total of 46 evaluable patients

Study Schema

Treatment Plan:

All treatment to be administered as an outpatient

Decitabine 10 mg/m² IV over 1 hour days 1-5

Vorinostat 200 mg PO twice a day days 6-15

IL-2 activated donor NK cell infusion IV over 15 to 60 minutes day 17

IL-2 6 MU SQ for 3 doses beginning on day 17 (2 hours after NK cell infusion), then day 19 and day 22

- Repeat treatment course 6 to 8 weeks later unless unacceptable toxicity, medically unsafe, or evidence of rapid disease progression as defined in section 7.10
- Assess for disease response 4 to 6 weeks after 2nd treatment course
- Follow for survival and progression to AML for 1 year from enrollment

* A single donor apheresis will be collected on day 15 of course 1. Centralized cell processing will occur at the University of Minnesota utilizing overnight shipping for Mayo products (U of MN products will be held an extra 24 hours to match Mayo's timing). The NK cell product will be divided in two after processing, but before IL-2 activation. Half will be stored frozen until course 2. The remaining cells will be prepared for fresh administration on day 17 of course 1.

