6.0 Patient/Donor Enrollment (On Study)

Enrollment onto the study will occur after the patient has signed the patient consent and eligibility is confirmed, but before any treatment has been administered. Any patient signing consent, but not registered in the study, will be recorded as a screen failure in the screening log as detailed in the study's Affiliate Manual.

To be eligible for enrollment to this study, the patient must meet each criteria listed on the eligibility checklist based on the eligibility assessment documented in the patient's medical record. The eligibility checklists (patient - Appendix I,

donor – Appendix - II) can be found under attachments within the study in OnCore.

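### Inclusion 4.2.2 admits hypomethylating-agent failures that exclusion 4.15 disqualifies, and 4.2.1 and 4.2.2 define treatment failure differently

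*Combined protocol and SAP*

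**What the plan says.** **Texts that admit.** Inclusion 4.2.2 reads "Treatment Failure: Patients who have not responded to or whose disease has progressed on hypomethylating agents (azacitidine or decitabine), 7+3 type induction chemotherapy", and then adds immunosuppressive therapy. It sets no limit on hypomethylating cycles. The Synopsis, under prior treatment, likewise takes non-responders and patients "whose disease has progressed on hypomethylating agents (azacitidine or decitabine), 7+3 type induction chemotherapy, or immunosuppressive therapy such as ATG+CSA". Item 2 of the patient eligibility checklist (Appendix I) offers the same category as a tick-box.

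**Texts that bar.** Exclusion 4.15 reads "Prior hypomethylating treatment greater than 2 cycles or with documented treatment failure". Checklist item 15 repeats it.

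**Which text prevails.** Section 6.0 says "the patient must meet each criteria listed on the eligibility checklist". The checklist states that a yes to any exclusion item disqualifies the patient. No sentence exempts patients who enter under 4.2.2.

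**What failure means.** Inclusion 4.2.1, the untreated or minimally treated category, allows up to two hypomethylating cycles "without evidence of treatment failure as defined by progression to more advanced MDS Who classification or AML". Inclusion 4.2.2 counts non-response as well as progression. Exclusion 4.15 gives no definition.

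**Where the category is used.** Section 7.6 and footnote 5 of the calendar in 8.1.1 require a marrow before course 2 for patients who met 4.2.2. Section 9.0 plans to compare response between untreated or minimally treated patients and prior treatment failures.

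**The concern.** There are two linked defects.

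First, the same patient can be admitted by one criterion and disqualified by another, and both are on the form that controls registration. Applying item 15 shuts out patients whom 4.2.2 and the Synopsis say are under study, and removes them from the 9.0 comparison. Acting on 4.2.2 alone registers patients whom the checklist declares ineligible.

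Second, 4.2.1 and 4.2.2 are meant to be alternatives, but they rest on different ideas of failure. Some patients with two or fewer cycles therefore satisfy both. For them, the comparison group in 9.0 and the mid-treatment marrow in 7.6 depend on which box in item 2 is ticked.

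What is at stake is whom the response rate describes.

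**Working it through.** **The plan's own figures.** The point does not rest on a number, but the design in 13.1 was checked so that it can be set aside. Inputs from 13.1: 15 patients in stage 1, stop at 5 or fewer responders; 46 in total, negative at 18 or fewer; response rates 0.30 and 0.50. The probability of a positive trial at true rate p is the sum over x = 6 to 15 of P(Bin(15, p) = x) × P(Bin(31, p) ≥ 19 − x).

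- p = 0.30: 0.0499, against a stated type I error of 5%.
- p = 0.50: 0.803, against a stated power of 80%.

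The design reproduces and is not in dispute.

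**Eligibility check.** Take a patient exposed to hypomethylating agents, with no other failed treatment and with the outcome documented. Cross the number of cycles with the outcome, and apply 4.15 under each meaning of failure that Section 4.2 supplies.

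| Cycles | Outcome | 4.2.1 | 4.2.2 | 4.15, failure as in 4.2.1 | 4.15, failure as in 4.2.2 | Conflict |
|---|---|---|---|---|---|---|
| ≤ 2 | No failure | admits | – | not barred | not barred | none |
| ≤ 2 | Non-response | admits | admits | not barred | barred | depends on definition |
| ≤ 2 | Progression, same WHO class | admits | admits | not barred | barred | depends on definition |
| ≤ 2 | Progression to more advanced WHO class or AML | – | admits | barred | barred | certain |
| > 2 | No failure | – | – | barred | barred | none |
| > 2 | Non-response or any progression | – | admits | barred (cycle limit) | barred (cycle limit) | certain |

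**Reading the table.**

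1. In the last row the definition of failure is irrelevant, because the cycle limit alone disqualifies.
2. In the fourth row both meanings agree that the patient has failed, so 4.2.2 admits and 4.15 bars. The WHO-class half is enough for this; 4.1 separately requires a diagnosis of high risk MDS.
3. The second and third rows meet both 4.2.1 and 4.2.2. Whether 4.15 bars them turns on a term it leaves undefined.
4. A patient who failed 7+3 or immunosuppressive therapy is admitted by 4.2.2. Exclusion 4.15 does not touch that patient unless there was also more than two hypomethylating cycles or a documented hypomethylating failure.

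**Can 4.15 be read narrowly?** One could confine it to the minimally treated category. That adds words it does not contain. It would also leave 4.15 with nothing to do, since 4.2.1 already carries both the two-cycle limit and the no-failure condition.

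**The case against.** The best defence is that the intent is plain. Sections 7.6, 8.1.1 and 9.0 expect prior failures on study, and the revision log records a widening of eligibility to previously treated, refractory patients, so 4.15 looks like a leftover. Intent to enrol some prior failures can indeed be inferred. It does not settle whether the two-cycle limit survives or which meaning of failure governs, and a log entry cannot override a current exclusion that staff must answer as written.

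Four stronger readings are tempting and are not supported.

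- **That 4.15 empties the failure group.** Failures of 7+3 or immunosuppressive therapy can still enter, and they alone could satisfy 7.6, 8.1.1 and 9.0. Those sections therefore do not by themselves prove the hypomethylating conflict.
- **That Appendix VI supplies a third meaning of prior failure.** Its failure category includes "disease progression characterized by worsening cytopenias, increase percentage of marrow blasts, or progression to a more advanced MDS FAB subtype", but it is an on-study response category that also counts death during treatment. Neither 4.2 nor 4.15 refers to it. Likewise, the Synopsis summarises the category that 4.2.1 defines; leaving out the definition is not a separate inconsistency.
- **That the two institutions will certainly apply the rules differently.** Section 6.1 has site staff complete the checklist, but for more than two cycles its answer is determinate: not eligible. Variation is plausible mainly for patients with two or fewer cycles, and it remains an inference.
- **That the trial's power is compromised.** The documents give neither the number of hypomethylating failures nor a response rate for them, so no such effect can be calculated without invented inputs.

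**Conclusion.** The plan is wrong as written and must be corrected. Three texts admit hypomethylating-agent failures (4.2.2, the Synopsis, checklist item 2), two disqualify them (4.15, checklist item 15), and none reconciles the two positions.

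The contradiction holds under either Section 4.2 meaning of failure for more than two cycles with non-response or progression, and for two or fewer cycles with progression to a more advanced WHO class or AML. For two or fewer cycles with non-response or same-class progression it is conditional on the meaning that 4.15 intends, and for these patients the prior-treatment group is ambiguous as well.

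This rests on the current text alone, and on taking the failure as documented. The number of patients affected cannot be derived from the documents.

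**What to change.** Reconcile 4.2.1, 4.2.2, 4.15, checklist items 2 and 15 and the Synopsis so that they state one population. Adopt one definition of prior treatment failure and use it in 4.2.1, 4.2.2 and 4.15, so that every eligible patient falls into exactly one prior-treatment group. State explicitly whether the two-cycle limit applies to patients entering as treatment failures. Which population and which definition apply is for the sponsor to decide.

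Sections 7.6, 8.1.1 and 9.0 can keep their present references once the categories no longer overlap.

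The cost is a wording amendment. It needs no extra patients, no new data and no change to the Simon boundaries.
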